## 9. Study Calendars

Baseline evaluations are to be conducted within 14 days prior to start of protocol therapy. Labs must be done prior to treatment on day 1 and maybe used for screening purposes as well. Scans and X-rays must be done <4 weeks prior to the start of therapy. In the event that the patient's condition is deteriorating, laboratory evaluations should be repeated within 48 hours prior to initiation of the next cycle of therapy.

### TP-0903 monotherapy, (Cycle 1 only)

	Screening*	Induction														End-of-Treatment 	Follow-up 				
		D1	D2	D3	D4	D5	D6	D7	D8	D9	D10	D11	D12	D13	D14	D15	D16	D18	D21	D28	
Medical History	x																			x	
Complete Physical exam and ECOG PS	x																			x	x
Weight and BSA	x	x				x												x	x	x	
Symptom directed physical evaluation		x				x						x					x		x	x	
Vitals signs 	x	x				x						x						x	x	x	x
12-Lead Electrocardiogram (ECG) 		x	x																	x	
Serum pregnancy test 	x																			x **if fertile female only	
CBC 	x	x				x						x						x	x	x	x
Complete Serum chemistry 	x	x				x						x						x	x	x	x
Coagulation tests (PT and PTT)	x	x				x						x								x	
TP-0903 dosing in Clinic/Home/Inpatient 		x	x	x	x	x	x	x	x	x	x	x	x	x	x	x	x	x	x		
Bone Marrow (BM) aspiration and biopsy 	x					x												x			

Adverse event and Toxicity evaluation 	x				x					x				x	x	x	
Correlative Studies 	x	x			x					x				x	x		

\* \*Treatment may begin on the same day as screening.

 Vital signs including blood pressure [BP], heart rate [HR], respiratory rate [RR], temperature [T] pulse oximetry (POX) and weight will be assessed prior to administration of TP-0903.

 ECGs: to be performed in the supine position at screening and day 1 of the first cycle.

 Applies to women of childbearing potential (WOCP) only. WOCP must have a negative pregnancy test within 2 weeks prior to the initiation of therapy.

 Complete Blood count with differential will be performed about twice weekly during induction and then as clinically indicated.

 Complete serum chemistries includes: Sodium, Potassium, Chloride, Bicarbonate, Creatinine, BUN, Glucose, Phosphorus, Albumin, Total bilirubin, SGOT (AST), SGPT (ALT), Alkaline phosphatase and LDH Women of childbearing potential must have a negative pregnancy test within 2 weeks prior to the initiation of therapy.

 TP-0903 will be administered per section 3.

 Bone marrow (BM) core biopsy and aspiration which will include cytogenetics, flow cytometry, targeted mutational analyses and morphologic assessment. Aspirate (10ml) only is required on day 5 of cycle 1 for correlative studies. Cycle 1, day 28 BM examination will require 10 ml aspirate to be collected for correlative studies. All the specimens for correlative studies will be processed at the OSU Leukemia Tissue Bank. Aspiration only may be acceptable for patients with BM biopsy that falls out of the window, provided AML diagnosis is unequivocal.

 Logistical issues that preclude patient visit on days noted will be allowed under special circumstances but must be discussed with the PI. Should such occasions arise, evaluations should be done as soon as feasible, preferably within 24-48hours

 Correlatives studies to be performed per section 8.2 (+/- 1 day). All patients will have serial peripheral blood sampling where cells are isolated at screening, day 5, day 12, at count recovery, at day 28 of each subsequent cycle (when available) and at time of relapse (in responding patients). Samples will be collected in green top (heparin tubes).

 End of Treatment visit, if applicable, is to be performed 30+7 days following patient last drug administration.

 Patients will be followed monthly for treatment failure until the time of transplant or maintenance therapy, at which time they will go to clinical follow-up, followed every 3 months for up to 2 years from registration and then every 6 months for up to 5 years from registration until relapse or death. Patients who end treatment for reasons other than relapse or a subsequent AML treatment (excluding transplant) will follow the same clinical follow-up schedule. Patients who relapse or receive a subsequent AML therapy (excluding transplant) will go to survival follow-up, followed every 6 months for 5 years from registration until death or the completion of the study. A survival follow-up visit can be conducted by phone or electronic contact with the patient or authorized representative.

TP-0903 monotherapy (Cycles 2-4 and maintenance)

	Cycles 2-4 and maintenance															End of Treatment 	Follow-up 		
	D1	D2	D3	D4	D5	D6	D7	D8	D9	D10	D11	D12	D13	D14	D15	D16	D18	D21	D28
Weight and BSA	x																x	x	x
Physical examination	x						x											x	
Vitals signs	x					x						x					x	x	x
12-Lead Electrocardiogram (ECG) 																		x	
CBC	x					x						x					x	x	x
Complete Serum chemistry	x					x						x					x	x	x
Coagulation tests (PT and PTT)	x											x						x	
TP-0903 dosing in Clinic/Home/Inpatient 	x	x	x	x	x	x	x	x	x	x	x	x	x	x	x	x	x		
Bone Marrow (BM) aspiration and biopsy 																	x		
Adverse event and Toxicity evaluation 	x											x					x	x	
Correlative Studies 																	x		

 ECGs to be completed on day 1 of cycles 2, 3 and 4 only. Subsequent ECGs for cycle 5 and later may be completed based on clinical judgment.

 TP-0903 will be administered per section 3.

 Bone marrow (BM) core biopsy and aspiration which will include cytogenetics, flow cytometry, targeted mutational analyses and morphologic assessment is required **only on Cycle 4, day 28**. BM examination on cycle 4, day 28 will require 10 ml aspirate to be collected for correlative studies. However, if the patient has persistent cytopenias or if there is concern for relapse, BM examination can be completed sooner based on clinical judgment. All the specimens for correlative studies will be processed at the OSU Leukemia Tissue Bank. Aspiration only may be acceptable for patients with BM biopsy that falls out of the window, provided AML diagnosis is unequivocal.

 Logistical issues that preclude patient visit on days noted will be allowed under special circumstances but must be discussed with the PI. Should

such occasions arise, evaluations should be done as soon as feasible, preferably within 24-48hours. Toxicity assessments on day 12 are only required for cycles 2-4. Cycles 5 and beyond require toxicity assessment only on days 1 and 2.

 If applicable, peripheral blood will be collected for correlative studies at day 28 of each subsequent cycle (when available) and at time of relapse (in responding patients). Samples will be collected in green top (heparin tubes).

 End of Treatment visit, if applicable, is to be performed 30+7 days following patient last drug administration.

 Patients will be followed monthly for treatment failure until the time of transplant or maintenance therapy, at which time they will go to clinical follow-up, followed every 3 months for up to 2 years from registration and then every 6 months for up to 5 years from registration until relapse or death. Patients who end treatment for reasons other than relapse or a subsequent AML treatment (excluding transplant) will follow the same clinical follow-up schedule. Patients who relapse or receive a subsequent AML therapy (excluding transplant) will go to survival follow-up, followed every 6 months for 5 years from registration until death or the completion of the study. A survival follow-up visit can be conducted by phone or electronic contact with the patient or authorized representative.

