### **1.8 Summary of clinical studies**

The first-in-human phase 1a/1b study with TP-0903, TP-0903-101 (Clinicaltrials.gov identifier: NCT02729298) is ongoing in patients with refractory solid tumors. The Phase 1a study is designed to identify the maximum tolerated dose (MTD) and to identify the safety profile and recommended phase 2 dose of TP-0903. Once the MTD has been established, 5 additional cohorts of up to 20 patients each with specific tumor type will be enrolled at the MTD in the phase 1b study. TP-0903 is administered once daily for 21 days followed by a 7-day drug-free period for one cycle. Patients are allowed to continue on TP-0903 if it shows benefit and is reasonably well tolerated. As of August 2018, adverse events observed in patients treated at the first 7 dose levels are shown in Table 2. Patients are consistently presenting with nausea/vomiting, diarrhea, and anorexia and no DLTs have been observed. Thus far, TP-0903 has been well tolerated with no patients coming off study due to drug-related toxicity. As of March 2019, a flat dose of 50 mg daily on days 1-21 of a 28 day cycle is the dose that will be used for future phase 1b expansion cohorts.

**Table 2.** Treatment-emergent adverse events by body system and preferred term by dosing cohort (safety population and overall).

MedDRA System Organ Class a MedDRA Preferred Term	BSA-based Dose (mg/m  )										Flat Dose (mg)
	Cohort 1 1.5 (n=3)	Cohort 2 3.0 (n=3)	Cohort 3 6.0 (n=3)	Cohort 4 9.0 (n=3)	Cohort 5 12 (n=3)	Cohort 6 16 (n=5 b )	Cohort 7 21 (n=3)	Cohort 8 28 (n=6)	Cohort 9 37 (n=6 c )	Cohort 10 50 (n=3)	
Metabolism and nutrition disorders (cont)											
Hypokalaemia	0	0	0	1 (33.3%)	1 (33.3%)	1 (20.0%)	0	0	1 (16.7%)	0	
Hyperglycaemia	0	1 (33.3%)	0	0	0	0	0	2 (33.3%)	0	0	
Hypocalcaemia	0	1 (33.3%)	1 (33.3%)	0	0	0	0	0	1 (16.7%)	0	
Hyponatraemia	0	0	0	1 (33.3%)	0	1 (20.0%)	0	0	0	0	
Musculoskeletal and connective tissue disorders											
Back pain	0	3 (100%)	0	0	0	2 (40.0%)	0	1 (16.7%)	2 (33.3%)	0	
Musculoskeletal pain	0	0	1 (33.3%)	0	1 (33.3%)	0	1 (33.3%)	1 (16.7%)	0	0	
Musculoskeletal chest pain	0	0	0	0	0	1 (20.0%)	1 (33.3%)	1 (16.7%)	0	0	
Myalgia	1 (33.3%)	1 (33.3%)	0	0	0	0	0	1 (16.7%)	0	0	
Nervous system disorders											
Dizziness	1 (33.3%)	0	0	0	0	3 (60.0%)	0	2 (33.3%)	0	0	
Dysgeusia	0	0	1 (33.3%)	0	2 (66.7%)	1 (20.0%)	0	1 (16.7%)	0	0	
Headache	0	0	0	1 (33.3%)	1 (33.3%)	0	0	1 (16.7%)	1 (16.7%)	0	

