Dehydration	0	0	0	0	2 (66.7%)	2 (40.0%)	1 (33.3%)	1 (16.7%)	1 (16.7%)	0	
Hypoalbuminaemia	0	1 (33.3%)	1 (33.3%)	0	0	1 (20.0%)	2 (66.7%)	1 (16.7%)	1 (16.7%)	0	
Hypomagnesaemia	1 (33.3%)	0	1 (33.3%)	2 (66.7%)	0	0	0	1 (16.7%)	1 (16.7%)	0	

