### **Non Hematologic:**

Any ≥ Grade 4 non-hematologic toxicity will be considered a DLT.

Any non-Hy's law ≥ Grade 3 liver abnormality is a DLT unless it resolves within 72 hours.

Any ≥ Grade 3 infection lasting more than 7 days in the absence of active AML is considered a DLT.

Any ≥ Grade 3 bleeding with thrombocytopenia in the absence of active AML is considered a DLT.

Any ≥ grade 3 non-hematologic toxicity not resulting directly from active leukemia is a DLT, with the exceptions of:

- Alopecia
- Line associated venous thrombosis
- Grade 3 fatigue, anorexia, constipation
- Grade 3 or 4 electrolyte disturbance that resolves within 24 hours with electrolyte correction and is not clinically significant,
- Grade 3 nausea or vomiting that does not require hospitalization or support with total parenteral nutrition and resolves to < grade 2 within 72 hours

The DLT observation period is defined as cycle 1 day 1 until completion of cycle 1 and will require that in the absence of DLT, patients receive at least 14 of the 21 planned doses of TP-0903 during cycle 1 to be considered evaluable for the tolerability check of the phase 1b. In other words, a patient will be considered unevaluable for the tolerability check and phase 1b component if a patient does not complete the DLT observation period due to reasons other than toxicity (e.g. progression). These patients will still be considered evaluable and included in the denominator when analyzing efficacy endpoints.

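### The defined serum chemistry panel omits magnesium and calcium, although the protocol's own TP-0903 safety table reports hypomagnesaemia (6/38) and hypocalcaemia (3/38)

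*Combined protocol and SAP*

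**What the plan says.** **Panel.** Section 9, Cycle 1 calendar, footnote 5: "Complete serum chemistries includes: Sodium, Potassium, Chloride, Bicarbonate, Creatinine, BUN, Glucose, Phosphorus, Albumin, Total bilirubin, SGOT (AST), SGPT (ALT), Alkaline phosphatase and LDH". That is 14 analytes, without magnesium or calcium. The calendar for Cycles 2-4 and maintenance has a row of the same name, with no footnote and no new definition. Section 5.1 refers to the chemistry that the protocol specifies and adds no analyte.

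**Earlier safety data.** Section 1.8, Table 2, lists treatment-emergent events from the first-in-human study in refractory solid tumours. The two relevant rows, for cohorts 1 to 10, read "Hypomagnesaemia 1 (33.3%) 0 1 (33.3%) 2 (66.7%) 0 0 0 1 (16.7%) 1 (16.7%) 0" and "Hypocalcaemia 0 1 (33.3%) 1 (33.3%) 0 0 0 0 0 1 (16.7%) 0".

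**Rules that use electrolyte values.**
- Section 4.1 makes non-hematologic toxicity of grade 3 or higher a DLT, subject to listed exceptions. One of them is "Grade 3 or 4 electrolyte disturbance that resolves within 24 hours with electrolyte correction and is not clinically significant".
- Section 4.2.1.1 holds treatment until recovery to grade 1 or lower, or to the patient's baseline.
- Section 5.2.1 counts as adverse events only those that are new or a worsening of an existing condition.
- The toxicity profile is a secondary objective. Section 10 summarises the maximum grade of each type of event per patient.

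**The concern.** The required laboratory panel does not match the drug's own safety table. Two electrolytes with reported treatment-emergent events are not on it, while rules elsewhere presuppose that electrolyte values exist.

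Three things follow if the plan is carried out as written:

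- A low magnesium or calcium comes to light only when someone chooses to order the test, so detection can depend on the clinician and the occasion.
- A low result found on treatment may have no screening value beside it. It then cannot reliably be classed as treatment-emergent, nor can a return to baseline be judged.
- The summarised rates of these two events would partly reflect how often the test was ordered.

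The high rate of gastrointestinal events in the upper cohorts of Table 2 adds to the reason for looking at electrolytes. What is at stake is the completeness of adverse-event ascertainment and of safety monitoring.

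**Working it through.** **Inputs.** Cohort sizes and counts come from Table 2, Section 1.8.

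Cohort sizes: 3+3+3+3+3+5+3+6+6+3 = 38.

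**Reproducing the table.** Dividing each hypomagnesaemia count by its cohort size gives 1/3 = 33.3%, 1/3 = 33.3%, 2/3 = 66.7%, 1/6 = 16.7% and 1/6 = 16.7%, as printed. The percentages in the other three electrolyte rows also match.

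**Totals for electrolyte terms.**

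| Term | Sum over cohorts 1 to 10 | Patients of 38 | On the panel? |
|---|---|---|---|
| Hypomagnesaemia | 1+0+1+2+0+0+0+1+1+0 | 6 (15.8%) | No |
| Hypokalaemia | 0+0+0+1+1+1+0+0+1+0 | 4 (10.5%) | Yes |
| Hypocalcaemia | 0+1+1+0+0+0+0+0+1+0 | 3 (7.9%) | No |
| Hyponatraemia | 0+0+0+1+0+1+0+0+0+0 | 2 (5.3%) | Yes |

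The text of Section 1.8 describes the table as covering the first seven dose levels, but ten cohorts are printed. In the first seven (n = 23) the counts are 4, 3, 2 and 2, so hypomagnesaemia still ranks first.

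**Precision.** The exact (Clopper-Pearson) 95% limits for x of N are the 2.5% point of Beta(x, N-x+1) and the 97.5% point of Beta(x+1, N-x).
- Hypomagnesaemia, x = 6, N = 38: Beta(6, 33) and Beta(7, 32) give 6.0% to 31.3%.
- Hypocalcaemia, x = 3, N = 38: Beta(3, 36) and Beta(4, 35) give 1.7% to 21.4%.

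**Gastrointestinal events in the two highest cohorts (6+3 = 9 patients).** Vomiting: 6+3 = 9 of 9. Diarrhoea: 3+2 = 5 of 9.

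**Illustration for 31 evaluable patients.** This assumes that the any-grade rate, pooled over all doses in solid tumours, carries over to AML at this trial's dose.
- Hypomagnesaemia: 31 × 0.060 = 1.9 to 31 × 0.313 = 9.7, so about 2 to 10 patients.
- Hypocalcaemia: 31 × 0.017 = 0.5 to 31 × 0.214 = 6.6, so about 0.5 to 7 patients.

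These are any-grade counts. They say nothing about how many events would reach grade 3.

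**Rules against measurements.** Classifying an event as new or worsened (Section 5.2.1) needs a value before treatment. Judging a return to baseline (Section 4.2.1.1) needs the same value and a later one. Applying the electrolyte exception (Section 4.1) needs a graded value and a repeat. For magnesium and calcium the plan requires none of these.

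**The case against.** The strongest case on the other side accepts the omission and disputes its consequence.

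- **The list may not be closed.** The footnote says that the panel includes these analytes, and local laboratories may report more. This stands as far as it goes: the text does not forbid the two tests. It does not require them either, and nothing in the documents says that they will be run.
- **There are other routes into the data.** Section 5.2.1 counts clinically significant laboratory abnormalities as adverse events, Section 5.3.2 records those found by any means, and Section 5.1 asks for consistency with institutional standards. So a clinically apparent event can be recorded. Unprompted findings and baselines remain unsecured.
- **The evidence for a drug effect is weak.** Table 2 gives no attribution. The ranking rests on 6 against 4 patients. Four of the six hypomagnesaemia cases are in cohorts 1 to 4, each term has 1 of 9 in the two highest cohorts, and both have 0 of 3 in the 50 cohort. All of this stands, although 0 of 3 has an exact 95% upper limit of 1 - 0.025^(1/3) = 71% and so reassures little. The term ranks first among electrolytes only: dehydration and hypoalbuminaemia have 7 each.
- **The DLT link is limited.** A reader might infer that the omission hides DLTs and biases the rule allowing at most one DLT in six patients. The documents do not support that. Table 2 has no grades, and Section 1.8 reports no DLTs in the data it describes. Electrolytes enter the DLT definition only through a conditional exception.
- **The 24-hour check is not special to these analytes.** A reader might also infer that the exception cannot be applied to magnesium and calcium in particular. Chemistry is not scheduled daily, so confirming resolution within 24 hours needs unscheduled repeats for sodium and potassium as well. Adding two analytes at the marked visits would not change that.

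**Conclusion.** The point holds as a gap in required measurement. The only panel definition names neither magnesium nor calcium, no other section requires them, and the protocol's own table reports hypomagnesaemia in 6/38 (15.8%, 95% CI 6.0 to 31.3) and hypocalcaemia in 3/38 (7.9%, 95% CI 1.7 to 21.4). As a result, ascertainment of these two events for the toxicity profile, and of any grade 3 or 4 event that would fall under the electrolyte exception, is not systematic, and a baseline may be missing.

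The size is modest and uncertain. The figure of about 2 to 10 patients with hypomagnesaemia among 31 rests wholly on carrying a pooled any-grade rate across doses and diseases. No number of missed DLTs and no bias in the tolerability decision can be derived from the documents. The events should be called treatment-emergent events observed with TP-0903, not established effects of the drug. The case for measuring does not depend on the exact ranking or rate. This is a cheap improvement, not a flaw in the design.

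**What to change.** Add magnesium and calcium to footnote 5 of the Cycle 1 calendar, so that both are measured at screening and at every chemistry time point already marked. Attach the same footnote to the chemistry row of the calendar for Cycles 2-4 and maintenance, so that one definition governs both. Albumin is already on the panel and helps in reading calcium.

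The cost is two further assays on blood already drawn and a short calendar amendment. Slightly more laboratory adverse events will be recorded. No visit, dose or clinical rule changes.

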## 10. Statistical Considerations

### Overview

This phase 1b/2 study will be conducted in adult relapsed/refractory AML patients with FLT3 mutations treated with TP-0903 monotherapy.

The study will open to accrual initially to confirm tolerability of TP-0903 monotherapy using 50 mg daily. If in the first 6 patients treated, tolerability is not confirmed, then an additional 6 patients will be treated using 37 mg daily. Once a tolerable dose level of TP-0903 monotherapy is confirmed, full accrual to the phase 2 portion of the trial will continue. Design details described below assume that TP-0903 monotherapy of 50 mg daily will be found tolerable.

### Confirmation of Tolerability

TP-0903 monotherapy has been evaluated in solid tumors and found to be safe at a dose level of 50 mg daily. Although we do not anticipate any safety challenges in patients with AML at this dose level, an early tolerability assessment will be included for the first 6 patients enrolled based on a standard Rolling 6 design. If at most one in 6 patients has a DLT (See Section 4), then TP-0903 monotherapy at 50 mg daily will be considered safe and we will proceed with full accrual of the phase 2 study. If however TP-0903 monotherapy at 50 mg daily does not have acceptable toxicity in the first 6 patients, then an additional 6 patients will be treated at a lower dose level of TP-0903 at 37 mg daily, and the same rule will be used to confirm tolerability. Once a tolerable dose level is confirmed, enrollment can continue to the phase 2 component at that dose level.

### Phase 2

At the confirmed tolerable dose level, TP-0903 monotherapy will be assessed for efficacy in a phase 2 component. Efficacy data from patients treated at the confirmed tolerable dose level during the tolerability check will be utilized in the phase 2 portion of the trial. Efficacy will be assessed using Simon's optimal two-stage phase 2 clinical trial design constraining type I and II errors to 10%.

The primary endpoint is the composite CR rate (CR/CRh), defined according to the 2017 ELN AML Recommendation. All eligible patients who start therapy will be considered evaluable for the primary endpoint and included in the denominator when calculating the composite CR rate. In relapsed/refractory adult patients with AML and FLT3 mutations, the ADMIRAL phase 3 study reported a composite CR rate of 34% with the FLT3 inhibitor gilteritinib, which led to improved overall survival (REF). We will therefore test the null hypothesis that the composite CR rate with TP-0903 is 30% versus the alternative hypothesis that it is 55%. By design, if 13 or more of 31 evaluable patients achieve CR/CRh, then there will be sufficient evidence to warrant further study of TP-0903 in this patient population. An interim analysis will occur after 13 patients have response determined. If 4 or fewer of 13 evaluable patients achieve CR/CRh, then the study will be terminated early. If 5 or more of 13 evaluable patients achieve CR/CRh then enrollment will continue as planned for all 31 evaluable patients. The probability of early termination under the null hypothesis is 0.65.

Toxicity will continue to be monitored throughout the phase 2 component, and a rule for excessive toxicity will be continuously applied. The monitoring rule will be evaluated during the first cycle of

therapy and will be based on the number of patients with a DLT out of the total number of patients treated (See Table Below). The number of patients with a DLT that would warrant accrual suspension corresponds to a high posterior probability that the true DLT probability is greater than an acceptable level (i.e.,  $\Pr(p_i > 0.25 | \text{data}) > 0.95$ ), where the posterior probability is determined from a *Beta-Binomial* distribution with *Beta* (1, 1) as the prior on  $p_i$ . For example, if 9 patients have been treated in the phase 2 study, and 5 or more patients have a DLT, then this is sufficient evidence of excessive toxicity and accrual will be suspended while data are reviewed more closely, and a decision will be made to modify or close the study.

**Table:** Excessive Toxicity Rule, following the Confirmation of Tolerability in the First 6 Patients

Number of Patients	7	8	9	10	11	12	13	14	15	16
Number with DLT	4	4	5	5	6	6	6	7	7	7
Number of Patients	17	18	19	20	21	22	23	24	25	26
Number with DLT	8	8	8	9	9	9	10	10	10	11
Number of Patients	27	28	29	30	31					
Number with DLT	11	11	12	12	12					

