## **Study Objectives**

### ***Primary Objectives***

- To determine a tolerable dose of TP-0903 monotherapy for relapsed/refractory patients with **FLT3 AML**.
- To determine the complete remission (CR) or complete remission with partial hematologic recovery (CRh) rate following induction therapy with TP-0903 in relapsed/refractory patients with **FLT3 AML**.

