#### **TP-0903 MONOTHERAPY FOR AML PATIENTS WITH FLT3 MUTATIONS AND RELAPSED/REFRACTORY DISEASE**

AML patients with FLT3 mutations and relapsed/refractory disease are eligible to receive TP-0903, at a starting dose of 50 mg daily as a single agent for days 1-21 of a 28-day cycle. If the 50 mg dose does not meet the tolerability criteria, a lower dose level of 37 mg daily as a single agent for days 1-21 of a 28-day cycle will be considered.

Dose Level	TP-0903 (D1-21) (mg/day PO)
-1	25
0	37
1	50

Patients may continue treatment indefinitely for as long as clinical benefit is achieved per the investigator's judgment. Bone marrow examinations for disease response assessment will be mandated after the first cycle and at the end of treatment. Subsequent bone marrow examinations may be completed at the discretion of the treating physician.

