### **3.1. Duration of Follow-up**

Patients will be followed monthly for treatment failure until the time of transplant or maintenance therapy, at which time they will go to clinical follow-up, followed every 3 months for up to 2 years from registration and then every 6 months for up to 5 years from registration until relapse or death. Patients who end treatment for reasons other than relapse or a subsequent AML treatment (excluding transplant) will follow the same clinical follow-up schedule. Patients who relapse or receive a subsequent AML therapy (excluding transplant) will go to survival follow-up, followed every 6 months for 5 years from registration until death or the completion of the study. A survival follow-up visit can be conducted by phone or electronic contact with the patient or authorized representative. Please see the study calendar in Section 9 for details.

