#### **4.2.1.2 Hematologic DLT:**

After the 42 day period and confirmed hematologic DLT: If peripheral blasts are absent AND bone marrow blasts are less than 5%, then the patient may restart study treatment on cycle 2 at the next lower dose level.

After achieving CR, the dose level may be re-escalated at the initiation of next cycle at the discretion of the investigator.

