### **7. Measurement of Effect**

#### **7.1. Response Criteria**

Assessment of clinical response will be made according to 2017 ELN AML Recommendation [1]. The major criteria for judging response will include physical examination and examination of blood and bone marrow. All laboratory studies that are abnormal prior to study will be repeated to document the degree of maximal response.

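### Does the missing response window for CR/CRh in Section 10 undermine the 4-of-13 stop and the 13-of-31 success rule?

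*Combined protocol and SAP*

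**What the plan says.** Section 10 (Phase 2) defines the primary endpoint as CR/CRh by the 2017 ELN criteria and puts every eligible patient who starts therapy in the denominator. It tests 30% against 55% with a Simon optimal two-stage design, both error rates capped at 10%. On timing it says only "An interim analysis will occur after 13 patients have response determined".

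Text bearing on when response is assessed:

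- Primary Objectives: the CR/CRh "rate following induction therapy with TP-0903 in relapsed/refractory patients with" FLT3 AML.
- Section 9, cycle 1 calendar: its columns are headed Induction and it covers cycle 1 only. A footnote says "Complete Blood count with differential will be performed about twice weekly during induction".
- Section 3: "Bone marrow examinations for disease response assessment will be mandated after the first cycle and at the end of treatment". Marrows beyond these are left to the physician.
- Section 3, on duration: "Patients may continue treatment indefinitely for as long as clinical benefit is achieved".
- Section 9, calendar for cycles 2-4 and maintenance: a marrow is required at cycle 4, day 28.
- Section 7.1, Treatment Failure: primary refractory disease depends on a period whose length is not given.

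**The concern.** A mandatory stop needs a clear count, and Section 10 does not say when the count is taken. It also does not say when a patient still on drug without remission becomes a non-responder. Several passages seem to allow later remissions:

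- Section 4.2.1.2, after a restart in cycle 2: "After achieving CR, the dose level may be re-escalated at the initiation of next cycle".
- Section 7.1: abnormal laboratory studies "will be repeated to document the degree of maximal response".
- Section 3.1: "Patients will be followed monthly for treatment failure until the time of transplant or maintenance therapy".
- Section 10: DFS starts at the first CR/CRh.

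If the window were chosen after outcomes were known in this single-arm trial, one patient could decide between stopping and continuing. The stated error rates also hold only if the 30% and 55% refer to the window actually used. In addition, Section 3 leaves marrows between cycle 1 and end of treatment to discretion, while the later calendar requires one at cycle 4, day 28.

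**Working it through.** **1. The plan's own figures.** Inputs from Section 10: n1 = 13, stop if X1 ≤ 4; n = 31, success if the total is ≥ 13; p0 = 0.30, p1 = 0.55.

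Early stop = P(X1 ≤ 4), X1 ~ Bin(13, p). At p = 0.30 the terms for 0 to 4 are 0.0097 + 0.0540 + 0.1388 + 0.2181 + 0.2337 = 0.6543. The plan states 0.65.

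Success = Σ over x = 5 to 13 of P(X1 = x) × P(Bin(18, p) ≥ 13 − x).

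| p | early stop | success |
|---|---|---|
| 0.30 | 0.6543 | 0.0875 (type I error) |
| 0.55 | 0.0698 | 0.9016 (power) |

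Both error limits are met. A search over two-stage designs up to n = 45 returns 4/13 and 12/31 as the optimal design. The arithmetic is sound, provided one response probability applies at both looks.

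**2. Which window the text supports.**

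| Text | Subject | Says that a remission after cycle 1 counts? |
|---|---|---|
| Primary Objectives | The endpoint itself, tied to induction | No |
| Section 9, cycle 1 calendar | The only calendar headed Induction | No |
| Section 3 | Response marrow mandated after cycle 1 | No |
| Section 3.1 | Visit schedule | No |
| Section 4.2.1.2 | Re-escalation of dose | No |
| Section 7.1, opening paragraph | Repeating abnormal laboratory studies | No |
| Section 10, DFS | Time origin of a secondary endpoint | No; fits any window |

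The first three rows concern when the primary response is assessed, and they agree on the end of cycle 1. The other four serve other purposes. They show that a later remission can happen, not that it enters the primary count.

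**3. What a mismatch would cost.** Assumption, not in the documents: 55% is a best-response rate and a share f of responders is documented by cycle 1, so the cycle 1 rate is 0.55f.

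| f | 0.55f | early stop | power, cycle 1 at both looks | power, cycle 1 at interim only | interim stops on cycle 1 data, best response in the same 13 would continue |
|---|---|---|---|---|---|
| 0.95 | 0.5225 | 0.101 | 0.848 | 0.874 | 0.031 |
| 0.90 | 0.4950 | 0.141 | 0.777 | 0.837 | 0.072 |
| 0.80 | 0.4400 | 0.251 | 0.581 | 0.734 | 0.181 |

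The last two columns split the first 13 patients into early, late and non-responders, with late conversion probability 0.55(1 − f)/(1 − 0.55f) among those not yet in remission.

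The error can also run the other way. If 30% is an early-window null, best response is counted, and the best-response null rate is 0.35 (assumed), the success probability is 0.221 instead of 0.0875.

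**4. The trade-off in moving the window.** Cycle 4 day 28 is day 4 × 28 = 112, which is 112 − 28 = 84 days after cycle 1 day 28, or about 2.76 months without cycle delays. At the 1-2 patients per month in the Accrual section, 2.8 to 5.5 more patients would enter before the futility decision unless accrual paused.

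**The case for a change.** The strongest opposing case is that the end-of-cycle-1 reading is inferred. The readable text never states the number of induction cycles. Cycles 2-4 are labelled neither induction nor maintenance, Section 10 does not mention induction, and the period in the refractory-disease definition is left blank. One sentence would settle it, and a binding stop arguably deserves that sentence.

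Most of this stands as a description: Section 10 is incomplete on timing. It does not establish an error. The treatment-plan and schema figures are missing from the copy reviewed and may show when response is assessed, so silence in the readable text is weak evidence. Nor would a non-responder stay undetermined indefinitely even under best response: treatment continues only while there is clinical benefit, progression is defined in Section 7.1, and an end-of-treatment marrow is mandated. The cost there would be delay.

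The marrow mismatch between Section 3 and the later calendar is real, and the two passages must be reconciled. It touches the primary count only if remissions after cycle 1 count, so it is an editorial matter here.

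**Conclusion.** This is missing detail that the trial's analysts can fill sensibly from the primary objective, the induction calendar and the mandated marrow: response at the end of cycle 1, used at both looks. On that reading, with 30% and 55% referring to the same window, the design keeps its type I error of 0.0875 and power of 0.902, and nothing is lost.

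The power losses (to 0.85, 0.78 or 0.58 for f = 0.95, 0.90 or 0.80) and the false-success figure of 0.22 need two things the documents do not supply: a share of late responders, and evidence that the hypothesised rates belong to another window. The window behind the cited 34% is not given, so no mismatch can be shown in either direction.

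A later cut-off would not be clearly better. It would capture late remissions but postpone a futility decision that stops an ineffective drug 65% of the time after 13 patients. That is a fair trade-off, and the text available leans towards the earlier assessment. The conclusion assumes that the figures not shown do not define induction differently.
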